1.2. Risk-Benefit Evaluation

This section gives risk-benefit evaluation for the conductance of the trial and for the use of VAR in the dose of 1 mg x 2 daily and BUP in the dose of 150 mg x 2 daily, in combination and alone.

Clinical and ethical standards

To give the best conditions possible for the safety of the study subject, the trial will be conducted in compliance with the ethical principles that have their origin in the Declaration of Helsinki and with the ICH Good Clinical Practice (GCP) guidelines.

Anticipated clinical benefits with VAR and BUP and B-PEth as used in the study

- The main benefit of the present study would be showing a superior treatment effect of the combination of drugs VAR and BUP, compared to VAR alone in AUD, which would be a first time finding. Further, if the effect size is 0.5-0.6 (Cohen's d), as hypothesized, this would represent the largest effect size observed for any available treatment of AUD.
- A second benefit would be confirming the treatment effect of VAR on alcohol consumption in AUD patients, which would represent the third study showing this effect.
- A third benefit would be showing a significant treatment effect of BUP on alcohol consumption in AUD patients, which would be a first time ever finding.
- A fourth benefit would be to demonstrate the superiority of B-PEth over self-report (in this case TLFB) for disclosing treatment effects in a second alcohol treatment trial. Such a finding may contribute to changing and improving the standards regarding primary outcome variables in alcohol treatment trials.
- A fifth benefit would be for the health care. Assessing the utility of B-PEth as biomarker will help clinicians screen for alcohol problems in a reliable fashion.

Health economic benefits

Consequences of high alcohol consumption impose tremendous suffering to the afflicted as well as burden on health and social care systems, and the annual costs to Swedish society have been estimated to at least 26 billion crowns (Socialstyrelsen, 2010). It is estimated that alcohol sequelae, i.e. consequences of alcohol, reduce life expectancy by 23 years (Lesch et al., 1986). The life-time risk of dying from alcohol-related causes (accidents and diseases) increases exponentially with alcohol consumption (Rehm, 2011). Not only abstinence but also reduction of alcohol intake profoundly lowers the risk of death in the heaviest consumers (Rehm and Roerecke, 2013). Many patients with AUD are not motivated for the abstinence goal but can accept the low risk drinking level goal (Hodgins et al., 1997; Heather et al., 2010). Focus has lately shifted from the abstinence goal in alcohol treatment trials to a goal of reducing alcohol consumption to lower risk levels (Mann et al., 2013; Nutt and Rehm, 2014). The present combination treatment, with expected effect size as described above, could lead to huge health economic benefits.

General benefits for the individual

By participating in the trial, the subject will:

- Get access to tentative new pharmacological treatments for AUD
- Help support medical science and help the development of treatments for AUD that can benefit people in the future
- Improve his/her own knowledge of the risks with excessive alcohol consumption and the nature of the disease
- Receive health status checked at no cost

Anticipated adverse drug reactions in the study

VAR and BUP are established and well-used prescription medication on the European and the US markets. The risks versus benefits regarding their approved indications nicotine dependence have previously been evaluated and are continuously being under evaluation. For all **Reference safety information** and full list on anticipated adverse drug reactions, go to Safety Section 7.1 and the SmPCs for VAR and BUP (Attachment 1 and 2).

Risk-Benefit Conclusion

Based on the clinical data on VAR and BUP in combination in the reference studies 1-7 (see Reference Safety Information, Section 7.1), the main expected AEs with VAR and BUP used in combination are:

- Sleep disturbance/insomnia
- Nausea
- Dizziness
- Vivid dreams

Based on the clinical data on VAR and BUP in combination in the reference studies 1-7 (see Reference Safety Information, Section 7.1), the main expected medical concerns are:

- An increased risk of seizures
- An increased risk of acute hypertension

Risk Benefit Conclusion

Based on the anticipated benefits of conducting the study as stated above, and the Reference Safety Information in Section 7.1, the Sponsor's judgment of the risk/benefit balance is that the benefits of conducting the trial justify the risks associated with the trial. The studies described above and clinical experience point to a good safety and tolerability profile of VAR and BUP, when used alone and when used in combination. Considering the frequent study visits and the exclusion of at-risk subjects for experiencing seizures we believe that the risks associated seizures will be mitigated or minimized. We judge that depressive side effects of VAR (previous a black box warning but not anymore) will be minimized by exclusion of depressive subjects and close follow-up. It is the Sponsor's judgment that the individual subject will benefit from the treatments and that the potential use of the study by far exceeds its tentative risks. Apart from the medical and psychosocial benefits for each alcohol dependent individual, a reduction in alcohol – and/or nicotine consumption may produce huge socioeconomic benefits to society in general, enhancing the significance of this trial. The Sponor's conclusion is that VAR and BUP will be safe and well tolerated in the present trial and states that the anticipated benefits justify the risks.

2. STUDY OBJECTIVES AND ENDPOINTS

2.1. Primary objective

To assess the effects of VAR and BUP in combination and alone for reducing alcohol consumption in individuals with AUD.

Two primary efficacy end-points will be used.

- 1) Alcohol consumption as measured by the objective alcohol marker B-PEth
- 2) Alcohol consumption as measured by heavy drinking days (HDD*) by using the Time Line Follow Back (TLFB) procedure

*HDD is defined as ≥ 60 grams for men and ≥ 40 for women according to EMA's guideline and as ≥ 70 grams for men and ≥ 56 grams for women according to FDA's guideline on the development of medicinal products for the treatment of alcohol dependence.

2.2. Secondary objective(s)

- 1) To assess the effects of varenicline and bupropion in combination and alone for reducing alcohol consumption in individuals with AUD by using
 - The indirect alcohol marker carbohydrate deficient transferrin (CDT)
 - The indirect alcohol marker gamma glutamyltransferase (GGT)
 - Self-reported alcohol consumption as measured by TLFB:
 - Mean grams of alcohol per day
 - Number of drinking days
 - Number of drinks per drinking days
 - Number of abstaining days
- 2) Total score of Alcohol Use Identification Test (AUDIT)
- 3) Alcohol craving as measured by a Visual Analogue Scale (VAS)
- 4) Nicotine use measured by the nicotine saliva marker cotinine
- 5) Temporal Experience of Pleasure Scale (TEPS)
- 6) The Continous Performance Test + Activity test (CPTA)
- 7) To assess the relationships between the above described outcome measures and plasma drug concentrations of bupropion and varenicline (measured at visits 4 and 6)

3. STUDY DESIGN AND PROCEDURES

3.1. Overall study design and flow chart

Design: The COMB-BO8 study is a Phase II, randomized, multicentre, double-blind, placebo-controlled trial with 4 parallel groups.

[figure not shown]
Trial Time Line COMB-BO8

Figure 2. Schematic time line for study visits. The study comprises a double-blind phase with 9 visits in total over 13 weeks (91 days). Day 0-7 is titration of dosing.

The required time for study participation is shown in table 2.

Visits	Day	Estimated time for visits	
Visit 1	Baseline	Medical visit/ Scr	3hrs
Visit 2	Day 0	Medical visit/Rand	1.5 hr
Visit 3	Day 7	Core battery visit	45 min
Visit 4	Day 21	Core battery visit	45 min
Visit 5	Day 35	Core battery visit	45 min
Visit 6	Day 49	Medical visit	1.5 hr
Visit 7	Day 63	Core battery visit	45 min
Visit 8	Day 77	Core battery visit	1.5 hr
Visit 9	Day 91	Medical visit/EoT	1.5 hr
All	-	Total time at Center	12 hrs

Table 2. Summary of time required for the study participant.

Follow-up phone calls are scheduled at Day 7 and Day 30 after End-of-Treatment
Phone call Day+ 7: 15 min.

Phone call Day+ 30: 15 min

The total time required from the trial subject, including the phone calls, is 12.5 hrs.

3.2. Rationale for study design

This trial assesses the efficacy of the established smoking cessation agents, VAR and BUP, on the new indication, AUD. The study assesses VAR and BUP alone and in combination, and is designed with 4 parallel groups to address the following hypotheses:

- Combination treatment with VAR and BUP reduces B-PEth levels and HDD from baseline and significantly more than placebo. The effect size, as measured by B-PEth, for the combined treatment is hypothesized to be 0.5-0.6 (Cohen's d).
- BUP reduces B-PEth levels from baseline and HDD from baseline and significantly more than placebo. The effect size, as measured by B-PEth, is hypothesized to be approximately 0.35 (Cohen's d).
- VAR reduces B-PEth levels from baseline and HDD significantly more than placebo. The effect size, as measured by B-PEth, is expected to be approximately 0.35 (Cohen's d).

Rationale for two primary End Points

Regulatory agencies will consider only one specific primary objective. The two primary endpoints fulfill regulatory requests independently and separately. HDD fulfill requirements for application of marketing approval. The biological marker is used to assess the reliability of PEth as End Point measure.

Rationale for the study design

A parallel group design will be used. A crossover design is not an option due to the risk that the beneficial effects of the first treatment will carry over into the second treatment period. The duration of a parallel-group trial is often shorter because only one treatment period is involved (yet a larger study group is needed). As in [name] et al. (de Bejczy et al., 2015) and Litten et al. (Litten et al., 2013) it is estimated that 12 weeks steady state duration will be adequate for detecting tentative effects, as measured by B-PEth and HDD, and at the same time be manageable for the participants, thus optimizing study compliance.

3.3. Study Visits

A full summary of the study visits in time is given in Table 1 in the Synopsis.

Recruitment

There are two modes of recruitment:

- Recruitment by advertising
Potential participants will be reached through a media campaign consisting of announcements in newspapers and/or an e-recruitment approach (a custom-made web-campaign outreach).
- Recruitment within the psychiatric/dependency clinics at the different study centers.

Pre-screening

There are two modes of pre-screening:

- In the advertisement, either web-based or in newspaper, the subjects will be asked to call the nearest study center for a telephone interview with staff trained to collect information about current drug and alcohol use pattern, current treatment regimens, demographics and health status. If eligibility criteria are met, an in-person screening visit is scheduled.
- Dissemination of information to interested participants will be done by medical staff at the study center clinics. Interested and eligible study subjects will undergo 30-minute telephone or face-to-face interview with trained staff to collect information about their current drug and alcohol use pattern, current treatment regimens, demographics and health status. If eligibility criteria are met, an in-person screening visit is scheduled.

Visit 1. Screening Visit. Accepted range: Maximum 14 days from prescreening

ID control is performed and breath alcohol level is determined to ensure sobriety (defined as blood conc. <0.1%). The participant may be offered a new screening visit, e.g. the following day, if sobriety is not fulfilled. Before any trial-related examination is performed, informed consent will be obtained. The subject will be informed orally of the aim of the trial, what participation entails and will be supplied with written information summarizing the details of the trial to read. Ample time will be given to the subjects to consider their participation. Agreement to participate in the trial will be confirmed by the subject signing and dating the Informed Consent Form (ICF). Documentation of the procedure is confirmed by delegated site personnel signing and dating the ICF. Medical history and alcohol anamnesis are collected and a physical examination is performed. Vital signs, safety and outcome specific blood samples and urine samples for pregnancy and toxicology will be collected. Alcohol consumption 30 days back in time will be documented by using the TLFB procedure. Baseline information is collected; demographics, alcohol and nicotine history, depression, and ADHD. The AUDIT and DUDIT will be administered. The Temporal Experience of Pleasure scale (TEPS) will be administered, and the Continuous Performance Test + Activity (CPTA) attention test will be performed via iPod. The eligibility criteria (except B-Peth criteria) will be evaluated by the medical doctor. If non-eligible and if required by medical condition the study seeking subject may be referred to appropriate clinic. If eligibility criteria are fulfilled, the subjects will be invited to a second visit within 8 days for randomization.

- Perform BrAC test by alcometer measuring alcohol concentration in exhaled air.
- ID control
- Perform the informed consent procedure, written and orally, confirmed by the subject signing and dating the ICF.
- Collection of medical history
- Collection of alcohol anamnesis and confirmation of alcohol diagnosis.
- Complete TLFB Alcohol calendar for 30 days preceding screening visit
- Collect AEs, if any
- Collect concomitant medication, if any
- Perform physical examination, which includes examination of armpits (lymph nodes), examination of mouth and throat, auscultation of heart and lungs, and palpitation of abdomen.
- Collect vital signs: Blood pressure and heart rate (after 10 min rest), length (at visit 1 only) and weight (at visit 1 and visit 9)
- Draw blood for safety parameters, AST, ALT, PC, glucose, creatinine, Na+/K+, Hb, LPK, TPK and hsCRP
- Draw blood for efficacy parameters B-PEth, CDT and GGT
- Perform dip stick tests for U-tox and U-hCG (pregnancy status, females only)
- Collect demographic data
- Complete questionnaires: VAS craving, AUDIT, DUDIT, ASRS, MADRS, Alcohol quantity frequency, nicotine quantity frequency and TEPS
- Administer CPTA test via iPod.
- Control and confirm (except B-Peth criteria) eligibility

Visit 2. Randomization Visit. Accepted range: Maximum 10 days from screening visit

The eligibility criteria based on blood sample analysis are checked and signed by medical doctor. If non-eligible and if required by medical condition the study seeking subject may be referred to appropriate clinic. The eligibility criteria are again confirmed. Medical status and concomitant medication is checked if case status has changed since screening. Data on alcohol consumption since last visit is collected by TLFB. Vital signs and blood samples for outcome specific measurements are collected. Urine sample for pregnancy and toxicology are collected. The subject is randomized to the trial and patient emergency card is handed out.

Saliva sample is collected for cotinine (nicotine metabolite) determination. The IMP is distributed according to randomization list. Patient emergency card is handed out. The study participants will be instructed to start taking the study drug on the following morning, the day after the randomization visit.

Before randomization

- Perform dip stick tests for U-tox, and pregnancy status (if applicable)
- Collect vital signs: Blood pressure, heart rate (after 10 min rest)
- Complete TLFB alcohol calendar since last visit
- Administer VAS craving questionairre
- Check and confirm that medical status is unchanged since screening visit
- Check and confirm eligibility criteria in eCRF system (in order to do this, all above measures must be entered in eCRF)
- Randomization
- Distribute patient emergency card
- Collect concomitant medications if any
- Collect AEs if any
- IMP distribution
- Perfrom saliva dip stick test for cotinine determination
- Collect blood for B-PEth, CDT and GGT analyses

Visit 3. Core battery visit. Accepted range +/- 3 days from scheduled visit date

AEs, data on concomitant medication, vital signs, and TLFB (data on alcohol consumption since last visit) are collected. Blood samples for alcohol specific outcome measures are drawn. IMP distribution.

Core battery

- Complete TLFB alcohol calendar since last visit
- Administer VAS craving questionairre
- Collect vital signs
- Collect AEs if any
- Record concomitant medication if any
- Collect blood for laboratory tests: B-PEth, CDT and GGT analyses
- IMP distribution, collection of IMP kits from last visit and drug accountability by pill count

Visit 4. Core battery and Safety visit. Accepted range +/- 3 days from scheduled visit date

AEs, concomitant medication, vital signs, and TLFB (data on alcohol consumption) are collected. Blood samples for alcohol specific outcome measures are drawn. Blood sampling for determination of IMP concentrations in blood will be performed before any dose is taken that day. The morning IMP dose will be given on site. The investigator will note in the CRF the time of the evening dose the day before was taken.

Core battery

- Complete TLFB alcohol calendar since last visit
- Administer VAS craving questionairre
- Collect vital signs
- Collect AEs if any
- Record concomitant medication if any
- Collect blood for laboratory tests: B-PEth, CDT and GGT analyses
- IMP distribution, collection of IMP kits from last visit and drug accountability by pill count.

Additional assessments

- Collect blood for safety tests: AST, ALT, PC and creatinine (Draw 10 ml blood)
- Administer MADRS (safety end point)
- Before the IMP dose is taken that day, collect blood for determination of VAR and BUP plasma concentrations (Draw 10 ml blood). The morning IMP dose will then be administered on site.

Visit 5. Core battery visit. Accepted range +/- 3 days from scheduled visit date

Adverse events, concomitant medication, vital signs, and TLFB (data on alcohol consumption) are collected. Blood samples for alcohol specific outcome measures are drawn. IMP distribution. Estimated time for visit is 1 hr.

Core battery

- Complete TLFB alcohol calendar since last visit
- Administer VAS craving questionairre
- Collect vital signs
- Collect AEs if any
- Record concomitant medication if any
- Collect blood for laboratory tests: B-PEth, CDT and GGT analyses
- IMP distribution, collection of IMP kits from last visit and drug accountability by pill count.

Visit 6. Optional Medical Visit Accepted range +/- 3 days from scheduled visit date

If judged as necessary by medical doctor or study participant, the subject is scheduled for a physician visit. Adverse events, concomitant medication, vital signs and TLFB (data on alcohol and nicotine consumption) are collected. Blood samples for alcohol specific outcome measures will be drawn. Blood sampling for determination of IMP concentrations in blood will be performed at Visit 6 before any dose is taken that day. The morning IMP dose will be given on site. The investigator will note in the CRF the time of when the evening dose the day before was taken. IMP distribution.

Core battery

- Complete TLFB alcohol calendar since last visit
- Administer VAS craving questionairre
- Collect vital signs
- Collect AEs if any
- Record concomitant medication if any
- Collect blood for laboratory tests: B-PEth, CDT and GGT analyses (Draw 15 ml blood)
- IMP distribution, accountability and check the returned medication kit from the last visit
- Consultation with medical doctor if requested

Additional assessment

- Before the IMP dose is taken that day, collect blood for determination of VAR and BUP plasma concentrations (Draw 10ml blood). The morning IMP dose will then be administered on site.

Visit 7. Core battery visit. Accepted range +/- 3 days from scheduled visit date

Adverse events, concomitant medication, vital signs, and TLFB are collected. Blood samples for alcohol specific outcome measures are drawn. IMP distribution.

Core battery

- Complete TLFB alcohol calendar since last visit
- Administer VAS craving questionairre
- Collect vital signs
- Collect AEs if any
- Record concomitant medication if any

- Collect blood for laboratory tests: B-PEth, CDT and GGT analyses (Draw 15 ml blood)
- IMP distribution, collection of IMP kits from last visit and drug accountability by pill count

Visit 8. Accepted range +/- 3 days from scheduled visit date

Adverse events, BrAC, concomitant medication, vital signs and TLFB (data on alcohol consumption) are collected. Blood samples for alcohol specific outcome measures are drawn. IMP distribution. Saliva sample is collected for cotinine determination. BrAC is determined. The TEPS will be administered and the CPTA test will be administered via iPod. AUDIT is administered.

Core battery

- Complete TLFB alcohol calendar since last visit
- Administer VAS craving questionnaire
- Collect vital signs
- Collect AEs if any
- Record concomitant medication if any
- Collect blood for laboratory tests: B-PEth, CDT and GGT analyses (Draw 15 ml blood)
- IMP distribution, collection of IMP kits from last visit and drug accountability by pill count

End of Analysis assessments

- Administer CPTA test via iPod
- Administer TEPS questionnaire
- Complete AUDIT
- Perform saliva dip stick test for cotinine analysis

Visit 9. End of Treatment/Medical visit. Accepted range +/- 3 days from schedules visit date

Medical examination by physician (30 min). AEs are collected as well as concomitant medication, vital signs and TLFB (data on alcohol consumption). Blood samples for alcohol specific outcome measures are drawn.

Core battery

- Complete TLFB alcohol calendar since last visit
- Administer VAS craving questionnaire
- Collect vital signs
- Collect AEs if any
- Record concomitant medication if any
- Collect blood for laboratory tests: B-PEth, CDT and GGT analyses (Draw 15 ml blood)
- Collection of IMP kits from last visit and drug accountability by pill count

End of Treatment and safety assessments

- Patient trial card collection
- Perform physical examination, which includes examination of armpits (lymph nodes), examination of mouth and throat, auscultation of heart and lungs, and palpitation of abdomen.
- Collect vital signs: Blood pressure, heart rate after 10 min rest, and weight (at visit 1 and visit 9)
- Draw blood for safety parameters, AST, ALT, PK, glucose, PK, creatinine, Na+/K+, Hb, LPK, TPK and hsCRP
- Perform drug of abuse test (U-tox)
- Administration of MADRS (safety endpoint)
- Complete DUDIT questionnaire (safety endpoint)

Follow-up Phone call (7 days after EoT)

Estimated time for phone call is 15 min.

- Collect/follow up AEs if any
- Record concomitant mediation if any
- Complete TLFB alcohol calendar data

Follow-up Phone call (30 days after EoT)

Estimated time for phone call is 15 min.

- Collect/follow up AEs if any
- Record concomitant mediation if any
- Complete TLFB alcohol calendar data for 7 days back in time

Extra study visits

If judged as required by the investigator, an extra study visit may be scheduled in addition to the ordinary study visits. The date, the reason for and the action taken at the visit must be documented in the CRF in a similar manner as for the pre-scheduled study visits. Additional blood (20 ml) will be drawn if judged as necessary.

Premature discontinuation

In the case of premature study discontinuation, an End-of-Treatment visit will be performed. In addition, any outcome measures at the ordinary visit that are not covered by the End-of-treatment visit will be collected (applicable for visit 4,6 and 8) . Discontinued subjects will also complete an AE report by phone call Day 7+ and, if AEs persist, at Day +30 (see Section 4.4).

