3.4. Study assessments

A summary of the study assessments in time is given in Table 1 in the Synopsis.

Investigator's training

The investigators and delegated qualified personnel will be trained in the study procedures, assessments and administration of scales required during the study. The training will be documented by a training certificate. The required scales and procedures for training are:

- Phone pre-screening
- The informed consent procedure
- Structured diagnostic interviewing
- The TLFB Alcohol procedure including interviewing technique
- Collection of AE and reporting of SAE
- Administration of study scales
- Handling of study specific medical device
- CPTA test administration on electronic device
- The electronic CRF system
- Study drug and randomization procedure
- Sampling, storing and sending procedure for blood analyses
- Procedure for study protocol violations and study drug non-compliance

Informed consent

Before enrolling the patient in the trial, i.e. before any trial-related examination is performed, Informed Consent must be obtained. Each potential participant will be informed, orally and in text, of the aim of the trial and what participation entails. They will be supplied with an Information Sheet summarizing the details of the trial. Ample time should be given to the patients to consider their participation. Agreement to participate in the trial is to be confirmed by the patient signing and dating the ICF. Documentation of this procedure is required. Documentation of the procedure is confirmed by the person who conducted the informed consent discussion signing and personally dating the ICF.

Breath alcohol concentration (BrAc)

BrAc will be measured at visit 1, to ensure sobriety during the informed consent and when performing the cognitive test (CPTA) and at visit 8, where CPTA is once again performed. BrAc is measured in exhaled air with a hand-held device, an Alcometer, and will provide an accurate estimate of the blood alcohol level. The Alcometer must be calibrated and documented, and used according the manufacturer's directions.

Demography

The demographic data that will be collected are: Gender and date of birth, civil status, number of children, and education. The age will be calculated in the eCRF.

AUD diagnosis

Documented diagnosis meeting ≥4 criteria according DSM-V by using structured interviewing.

Medical history

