4. STUDY POPULATION

4.1. Inclusion criteria

- 1) Signed informed consent
- 2) Blood alcohol level below <0.1‰ (0.1 g/L) at signing informed consent
- 3) 25-70 years of age at screening
- 4) Moderate and severe AUD according to DSM-V (meeting ≥4 out of 11 criteria)
- 5) B-PEth levels of ≥0.5 µmol/L at screening visit (visit 1) as defined by at least 2 HDD per week on a typical week.
- 6) Continuous high alcohol consumption over the last 3 months prior to screening
- 7) Available phone number for contact
- 8) Ability to speak and write in Swedish

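### Section 3.3 defines sobriety at the Visit 1 breath test as a blood concentration below 0.1%, ten times the 0.1‰ (0.1 g/L) limit in inclusion criterion 2

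*Protocol*

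**What the plan says.** Three places in the protocol bear on the alcohol limit at consent.

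- **Inclusion criterion 2 (Synopsis and Section 4.1, same wording):** "Blood alcohol level below <0.1‰ (0.1 g/L) at signing informed consent". The g/L figure fixes the unit.
- **Visit 1 procedure (Section 3.3):** "breath alcohol level is determined to ensure sobriety (defined as blood conc. <0.1", followed by a percent sign. No g/L equivalent is given. The breath test is the first action in the Visit 1 list and comes before consent. On failing it: "The participant may be offered a new screening visit, e.g. the following day, if sobriety is not fulfilled".
- **Description of the breath test (Section 3.4):** "BrAc will be measured at visit 1, to ensure sobriety during the informed consent", and also for the CPTA attention test. No number is given here. A second breath test at Visit 8 accompanies the repeat CPTA, also without a number.

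Section 8.2, under randomization issues, treats randomizing someone who does not meet the eligibility criteria as a protocol violation and leaves that person out of the analysis sets.

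**The concern.** Section 3.4 ties the Visit 1 breath test to consent, and criterion 2 is also defined at signing of consent. The two figures therefore govern one check, at one visit, for one purpose, and they do not agree. Nothing in the protocol reconciles them.

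Section 3.3 is the step-by-step instruction for the visit, and it is where the word sobriety is given a number. A site using it literally could pass someone whom criterion 2 excludes. Three things would then be affected:

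- a consent signed above the limit that the protocol itself sets;
- the baseline data taken at the same visit, namely the CPTA, the questionnaires and the 30-day TLFB calendar, which is the stated source of baseline heavy drinking days;
- the analysis sets, if the person went on to be randomized and the violation was recognized.

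The trial recruits people with continuous high alcohol consumption, so measurable alcohol at a screening visit is foreseeable.

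**Working it through.** This is a unit conversion. No sample-size, power or alpha figure is involved.

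**Inputs**

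- Criterion 2 (Synopsis; Section 4.1): 0.1‰, stated as 0.1 g/L.
- Visit 1 procedure (Section 3.3): 0.1%.

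**Step 1: reproduce the protocol's own equivalence.** On a weight-per-volume basis, with 1 L taken as 1000 g:

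0.1‰ = (0.1 / 1000) × 1000 g/L = 0.1 g/L.

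This matches the figure in criterion 2, so it is the basis the protocol uses.

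**Step 2: convert the Visit 1 figure on the same basis.**

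0.1% = (0.1 / 100) × 1000 g/L = 1.0 g/L = 1.0‰.

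**Step 3: compare.**

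1.0 g/L ÷ 0.1 g/L = 10.

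The ratio does not depend on the weight-per-volume convention, because a percent is ten per mille on any basis.

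**Step 4: what each rule does with a given value.**

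| Blood alcohol | Section 3.3 as printed | Criterion 2 |
|---|---|---|
| below 0.1 g/L | sober | met |
| 0.1 g/L to just under 1.0 g/L | sober | not met |
| 1.0 g/L or more | not sober | not met |

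The rules differ only in the middle row. The protocol gives no figure for how many attendees would fall there, and none is assumed.

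**The case against.** The strongest reply is that this is one character. The digits, the direction of the inequality and the purpose are the same in both places, so a percent sign typed for a per-mille sign is the natural explanation. It is also possible that the sign was misread when the PDF was converted to text. If the PDF prints a per-mille sign, the point falls away. The per-mille sign came through intact in both statements of criterion 2, which makes a misreading less likely but does not exclude it. This stands as a reason to check the PDF first.

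The second reply is that the governing rule is clear. Criterion 2 appears twice with a g/L value. The physician evaluates eligibility at Visit 1 (all criteria except B-PEth), and eligibility is confirmed again at Visit 2 and in the eCRF before randomization. This also stands: someone in the gap would have to pass all of these checks to be randomized. It lowers the likely frequency. It does not undo a consent already signed, and it does not remove the contradiction.

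Third, a reader might infer more than the text supports:

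- **That a looser consent standard was deliberately chosen.** Nothing in the protocol argues for one, and criterion 2 contradicts it.
- **That the trial's results are put at risk in proportion to the factor of ten.** Ten is the ratio of the limits, not the size of a consequence. B-PEth is a laboratory measure, the baseline TLFB is completed together with site staff, and the CPTA, for which Section 3.4 expressly wants sobriety, is a secondary measure.
- **That Visit 8 carries the same error.** No limit is stated there, so there is nothing to contradict.

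**Conclusion.** The inconsistency holds on the printed text. Section 3.3 sets 1.0 g/L where criterion 2 sets 0.1 g/L for the same pre-consent check, a factor of exactly ten. It is an error in an operating threshold, probably typographical, and not a design choice.

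Its reach is limited. Anyone between 0.1 and 1.0 g/L would count as sober under Section 3.3 and fail criterion 2. How many people that is cannot be derived from the protocol, and later eligibility checks would be expected to catch some of them. Sample size, power and alpha are untouched. It still deserves correction because staff act on the printed limit, the limit concerns consent, and the protocol's own rule would remove the affected people from the analysis sets if they were randomized.

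The conclusion assumes that the PDF does print a percent sign in Section 3.3 and that both passages use the unit basis that criterion 2 makes explicit. No view is taken here on which limit should stand.

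**What to change.** 1. Check the sign after 0.1 in the Visit 1 text of Section 3.3 against the protocol PDF.
2. If it is a percent sign, reconcile Section 3.3 with criterion 2 in the Synopsis and Section 4.1, so that one limit in one unit, with its g/L equivalent, appears in all three places. The sponsor decides and states the limit.
3. Optionally, state a limit for the Visit 8 breath test as well. This would be a clarification and is not part of the error.

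The cost is one symbol, plus a g/L figure in Section 3.3, in the next amendment. No analysis, sample size or visit schedule changes.
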